8.3.2.2. Congenital Anomalies/Birth Defects and Abortions

Any congenital anomaly/birth defect in a child born to a female subject or partner of a male subject exposed to study drug should be classified as an SAE and reported as such. Any spontaneous abortion or miscarriage should be reported in the same fashion (therapeutic abortions are excluded from expedited reporting and would be captured as pregnancy outcome information). Refer to [Section 8.2.5.11](#) for additional information regarding follow-up and SAE reporting requirements for exposure during pregnancy.

8.4. Follow-Up of Subjects After Adverse Events

8.4.1. Investigator Follow-Up

The Investigator should follow each AE until the event has resolved to baseline grade or better, the event is assessed as stable by the Investigator, the subject is lost to follow-up, or the subject

withdraws consent. Every effort should be made to follow all SAEs considered to be related to study drug or trial-related procedures until a final outcome can be reported.

During the study period, resolution of AEs (with dates) should be documented on the Adverse Event CRF and in the subject's medical record to facilitate source data verification.

All pregnancies reported during the study should be followed until pregnancy outcome.

8.4.2. Turning Point Therapeutics Follow-Up

For SAEs and pregnancies, Turning Point Therapeutics or a designee may follow-up by telephone, fax, electronic mail, and/or a monitoring visit to obtain additional case details and outcome information (e.g., from hospital discharge summaries, consultant reports, autopsy reports) in order to perform an independent medical assessment of the reported case.

8.5. Post-Study Adverse Events

Turning Point Therapeutics should be notified if the Investigator becomes aware of any SAE that occurs after the end of the AE reporting period (defined as 28 days after the last dose of study drug) if the event is believed to be related to the study drug.

The Investigator should report these events directly to Turning Point Therapeutics or its designee using the SAE Report Form.

8.6. Expedited Reporting to Health Authorities, Investigators, Institutional Review Boards, and Ethics Committees

Turning Point Therapeutics will promptly evaluate all SAEs against cumulative product experience to identify and expeditiously communicate possible new safety findings to Investigators, IRBs, ECs, and applicable health authorities based on applicable legislation.

To determine reporting requirements for single AE cases, Turning Point Therapeutics will assess the expectedness of these events using the IB.

Turning Point Therapeutics will compare the severity of each event and the cumulative event frequency reported for the study with the severity and frequency reported in the applicable reference document.

Reporting requirements will also be based on the Investigator's assessment of causality and seriousness, with allowance for upgrading by Turning Point Therapeutics as needed.

9. STATISTICAL METHOD ANALYSIS

Detailed methodology for summary and statistical analyses of the data collected in this trial will be documented in a Statistical Analysis Plan (SAP), which will be maintained by the Sponsor or their designee. The SAP may modify the initial analysis plan outlined in the protocol; however, any major modifications of the primary endpoint and/or analysis methods will also be reflected in a protocol amendment.

9.1. Analysis Sets

9.1.1. Full Analysis Set

The Full Analysis Set (FAS) consists of all subjects who receive at least one full or partial dose of both study drugs. This will be the same as the Safety Analysis Set. The FAS set will be used for the summary of subject disposition, demographics, and baseline characteristics, and safety analysis. For Phase 2, the FAS set will also be used for primary efficacy analysis if subjects have received repotrectinib.

Subjects will be classified according to the assigned treatment dose levels. Subjects who were screened but never started treatment will be listed in the subject data listing as screening failure, and reasons for screening failure will be included.

9.1.2. Efficacy Evaluable Analysis Set

Efficacy Evaluable (EE) Analysis Set will include all enrolled subjects who (1) have received at least one dose of study treatment with repotrectinib; (2) *KRAS* mutation determined by a qPCR or NGS test performed in a CLIA laboratory or equivalently accredited diagnostic laboratory; (3) have a baseline tumor assessment with measurable disease and have at least 1 on-study tumor assessment per RECIST v1.1; and (4) have no major protocol violations that could affect efficacy.

The EE Analysis Set will be used for efficacy analyses for Phase 1b, and sensitivity analysis of efficacy endpoints for Phase 2.

9.1.3. Safety Analysis Set

The Safety Analysis Set includes all enrolled subjects who receive at least one dose of either study drug. This will be the same as the FAS. Subjects will be classified according to the actual treatment (dose levels or cohorts). Each subject will be classified into and analyzed consistently within one treatment group, unless otherwise specified.

9.1.4. Pharmacokinetic Concentration Analysis Set

The PK Concentration Analysis Set is defined as all enrolled subjects who receive at least one dose of study drug and have at least one concentration of study drug.

9.1.5. Pharmacokinetic Parameter Analysis Set

The PK Parameter Analysis Set is defined as all enrolled subjects who receive at least one dose of study drug and have sufficient information to estimate at least one of the PK parameters of interest.

9.2. Sample Size Determinations

9.2.1. Repotrectinib + Trametinib

9.2.1.1. Phase 1b Dose Escalation

For dose escalation, 3 to 6 DLT-evaluable subjects will be enrolled per dose level. Therefore, it is expected that approximately 24 – 30 subjects will be enrolled to determine the RP2D of repotrectinib in combination with trametinib.

9.2.1.2. Phase 2 Expansion

For Phase 2 expansion, sample size will be determined using Pearson-Clopper exact confidence interval method. A total of approximately 50 subjects will be enrolled. In addition, up to 6 locally advanced or metastatic *KRAS*-mutant NSCLC subjects treated at the RP2D in Phase 1b will be pooled for the efficacy analysis. If 21 subjects out of 56 subjects have a confirmed objective response (ORR = 38%; 95% CI: 25 – 51) where the lower limit of the 95% CI is > 23%, repotrectinib in combination with trametinib will be considered superior than the currently approved chemotherapy in the second-line setting for NSCLC in this expansion cohort, including the combination of docetaxel + ramucirumab ([Cyramza® USPI, 2020](#)) which has demonstrated a best ORR of 23% (95% CI: 20 – 26) in the second-line setting.

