3.2. Phase 1b Dose Escalation Study Design

The Phase 1b dose escalation portion of the study will follow a traditional 3+3 design, where three to six DLT-evaluable subjects with locally advanced or metastatic *KRAS*^{G12D}-mutant solid tumors will be enrolled at each dose level to determine the MTD/RP2D of repotrectinib in combination with trametinib through assessment of DLTs.

Initially, approximately 24 – 30 subjects with locally advanced or metastatic solid tumor malignancies harboring a *KRAS*^{G12D} mutation will be enrolled into the Phase 1b dose escalation portion. Three to six DLT-evaluable subjects at each dose level will be administered daily (QD) doses of repotrectinib in combination with trametinib according to Table 2 (starting with Dose Level 1) and evaluated for DLTs during Cycle 1 (i.e., for 28 days). After the first 3 subjects have completed their first cycle of study treatment (Cycle 1), a safety evaluation will be conducted by a Safety Review Committee to determine if enrollment of subjects in the next dose level (Dose Level 2) may begin. If no subjects experience a DLT within the first 28 days of Dose Level 1 treatment, then dose escalation may proceed to the next dose level, according to Table 2. If 1 of the 3 initial subjects at Dose Level 1 experiences a DLT, then the next 3 subjects will be enrolled prior to escalating to the next dose level. Enrollment into all subsequent dose levels will follow

the same procedure. If $\geq 33\%$ of subjects at any dose level experience a DLT within the first 28 days of treatment, the dose levels will be de-escalated to Dose Level -2 or -3 according to SRC recommendation and following approval by the Sponsor, as detailed in [Table 2](#). If Dose Level -2 is tolerable, testing of alternate escalating dose levels (-2a, -2b) may occur as outlined in [Table 2](#). If Dose Level -2 is not tolerable, subjects will be de-escalated to Dose Level -3. If Dose Level -3 is tolerable, testing of alternate escalating dose levels (-3a, -3b) may occur as outlined in [Table 2](#). Alternative regimens or additional dose levels or dose level increments may be explored based on emergent clinical safety, efficacy, and PK data. See [Section 3.2.1.1](#) for criteria for determining DLTs. The decision to escalate to the next dose level will be based on the incidence of DLTs and the totality of clinical data including overall PK, safety, and preliminary efficacy observed within each dose level.

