3.2.1.3. Recommended Phase 2 Dose (RP2D) Definition

The RP2D is the dose chosen for further study in Phase 2 based on the Phase 1b results. RP2D dose selection will be based on the entirety of the safety, efficacy, and clinical pharmacology data using an integrated quantitative approach. The RP2D may be the MTD unless one or more of the following suggest an alternate dose below the MTD would be preferable:

- a. clinically significant anti-tumor effect (complete response [CR], partial response [PR], or prolonged stable disease [SD]) occurs below the MTD, in which case a clinically active dose level may be selected as the RP2D;
- b. the MTD is not achieved, in which case the highest dose level administered may become the RP2D; or
- c. toxicities observed beyond the DLT evaluation period (Cycle 1) require selecting the RP2D below the MTD level.

Once the MTD of repotrectinib in combination with trametinib has been determined, the RP2D will be determined at or below the MTD. At least 6 subjects will be treated at the RP2D prior to proceeding into the Phase 2 portion of the study. Additional subjects may be added at a dose level to gather more safety, PK, and efficacy data.

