9.4.3.1. Objective Response Rate

The ORR will be defined as the proportion of subjects with a confirmed CR or PR. A confirmed response is a response that persists on a repeat imaging performed at least 4 weeks after initial documentation of response. Subjects with a confirmed objective response (CR or PR) will be referred to as responders. Non-responders will include subjects without a confirmed objective response, SD, progressive disease (PD), not evaluable (NE), or non-CR/non-PD (NN). The ORR will be reported as the proportion of responders by RECIST v1.1 along with the corresponding two-sided 95% Clopper-Pearson exact CI.

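### The Phase 2 superiority rule does not say that the 23% confidence limit governs rather than 21/56, and it pools Phase 1b subjects who may have informed the dose without a prespecified Phase 2-only check

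*Combined protocol and SAP*

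**What the plan says.** Section 9.2.1.2 sizes Phase 2 by the exact confidence interval method. Enrolment is approximate: "A total of approximately 50 subjects will be enrolled". Up to six more come from the escalation part: "NSCLC subjects treated at the RP2D in Phase 1b will be pooled for the efficacy analysis". The superiority conclusion over approved second-line chemotherapy is then attached to two things in one sentence: "If 21 subjects out of 56 subjects have a confirmed objective response", with a printed ORR of 38% (25–51), and "where the lower limit of the 95% CI is > 23" per cent. The 23% is the ORR quoted for docetaxel plus ramucirumab. The synopsis repeats the statement. Section 9.4.3.1 reports the ORR "along with the corresponding two-sided 95% Clopper-Pearson exact CI". Section 9.5 names 38% as the target ORR.

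Phase 1b enrols "subjects with locally advanced or metastatic solid tumor malignancies harboring a" *KRAS* G12D mutation (Section 3.2), so how many NSCLC subjects at the RP2D will be available is not known in advance. Section 3.2.1.3 bases the RP2D on safety, efficacy and clinical pharmacology together. If anti-tumour effect is seen below the MTD, it describes a situation "in which case a clinically active dose level may be selected as the RP2D". It also says: "Additional subjects may be added at a dose level to gather more safety, PK, and efficacy data".

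Sections 9.1.1 and 9.4.3 make the FAS primary for Phase 2 efficacy. Sections 9.1.2 and 9.4.3 assign Phase 1b efficacy to the EE set. None of the three mentions the pooled subjects.

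**The concern.** This is the only stated rule for calling the combination superior to second-line chemotherapy. It raises two separate issues.

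First, the sentence gives a count and a confidence limit and does not say which decides. If the count were only the smallest number meeting the limit, the two would coincide, but they do not. No count is given for any N below 56, although 56 is the maximum under the planned figures. A result of 20 responders at N = 56 could therefore be argued either way once the data are known.

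Second, the same responses may be used twice: once to help choose the RP2D and again in the test at that dose. If good responses make a level more likely to be chosen, the responses of its subjects are, on average, too favourable given that it was chosen. The protocol text prespecifies no ORR that leaves those subjects out.

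**Working it through.** **Inputs.** From Section 9.2.1.2: about 50 Phase 2 subjects plus 0 to 6 pooled, benchmark 23%, 21/56. From Section 9.4.3.1: two-sided 95% Clopper-Pearson. From Section 9.5: target 38%, and a futility stop at 2 or fewer responders among 15. Taking 23% as the null rate is my choice; the protocol states no type I error or power for this rule.

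**1. The plan's own figure.** For x responders of N, the lower limit is the 0.025 quantile of Beta(x, N − x + 1) and the upper limit is the 0.975 quantile of Beta(x + 1, N − x). For 21/56 = 37.5% this gives 24.92–51.45%, which rounds to the printed 38% (25–51). The figure reproduces.

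**2. Is 21 the minimum?** 20/56 = 35.7%, CI 23.36–49.64%, clears 23%. 19/56 has lower limit 21.81% and fails. The minimum at N = 56 is 20.

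**3. Minimum count at each possible N under the CI limit.**

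| N | Minimum | Lower limit | Lower limit, one fewer |
|---|---|---|---|
| 50 | 19 | 24.65% | 22.92% |
| 51 | 19 | 24.13% | 22.43% |
| 52 | 19 | 23.62% | 21.97% |
| 53 | 19 | 23.14% | 21.52% |
| 54 | 20 | 24.29% | 22.68% |
| 55 | 20 | 23.81% | 22.24% |
| 56 | 20 | 23.36% | 21.81% |

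**4. What the two readings do at N = 56** (exact binomial tails).

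| Rule | P(success), ORR 38% | One-sided error, ORR 23% |
|---|---|---|
| 20 or more | 0.685 | 0.0214 |
| 21 or more | 0.581 | 0.0103 |

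The difference at 38% is P(X = 20) = 0.104. With the futility stop applied to the first 15 Phase 2 subjects, the figures are 0.675 and 0.0208 against 0.575 and 0.0101.

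**5. Pooled against Phase 2-only, with no selection.** Let X ~ Bin(50, p) and Y ~ Bin(6, p) be independent. Pooled success is X + Y ≥ 20; Phase 2-only success is X ≥ 19.

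| True ORR p | Both | Pooled only | Phase 2 only | Verdicts differ |
|---|---|---|---|---|
| 23% | 1.08% | 1.06% | 0.14% | 1.2% |
| 30% | 13.4% | 7.9% | 0.7% | 8.6% |
| 38% | 54.7% | 13.8% | 0.7% | 14.5% |

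Phase 2-only success at 38% is 0.547 + 0.007, about 55%. These figures do not measure bias, because no selection was assumed. They reflect mainly the move from 50 to 56 subjects. For example, 18/50 = 36.0% fails (22.92%) and 20/56 = 35.7% passes (23.36%), although the second rate is slightly lower. Pooling can also hurt: 19/50 passes (24.65%), but adding 0/6 gives 19/56, which fails.

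**6. Selection.** If choosing the dose partly on response raises the expected rate in the six pooled subjects by d, the pooled ORR rises by (6/56)d = 0.107d. The documents give no basis for d. Purely as an assumed range, d = 5 to 20 percentage points would move the pooled ORR by 0.5 to 2.1 points.

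**The case against.** On the threshold, the plan names the exact CI method before it gives the count, and 21/56 rounds to the 38% target. The natural reading is that 21/56 illustrates the limit at the target ORR. Nothing calls 21 a minimum. That stands, so the issue is unstated intent and not a wrong number. A reader might infer that the printed interval is wrong or that error control is lost; neither is so. A reader might also turn 21/56 into a 37.5% threshold for other N, but the documents state no proportion rule.

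On pooling, the plan announces it in advance and caps it at six. Safety and PK also drive the RP2D, and subjects added after the dose is chosen carry no selection bias. That stands too. A reader might take the 13.8% in step 5, or the 18/50 against 20/56 example, as evidence of selection; both arise without any. A reader might also want an error rate under selection. Assuming six NSCLC subjects at each of two to four levels, a true ORR of 23% at all of them, and a dose chosen on responses alone, P(lower limit > 23%) would be 3.0–4.1% instead of 2.1%. Those assumptions do not fit an all-solid-tumour escalation of about 24–30 subjects with three to six evaluable per level, or an RP2D based on all the data. The figure is not an estimate for this trial.

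On the analysis set, the pooling sentence sits under Phase 2, where the FAS is primary, and Section 3.2.1.1 keeps subjects replaced for DLT evaluation in the efficacy analyses. FAS is the straightforward reading. One can build a reversal (19/56 fails, 19/53 passes at 23.1%), but it needs three of six pooled subjects without an on-study scan and a proportion that mixes two analysis sets.

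Finally, Section 9.4.1 defers detail to a SAP whose text is not in the supplied document. The absence of a Phase 2-only analysis can therefore be stated only for the protocol text. The superiority rule itself is in the protocol, so its wording can be settled there.

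**Conclusion.** The point holds in limited form and should be corrected before the data are seen. The governing rule is not stated. At N = 56 and a true ORR of 38%, the two readings disagree in about 10% of trials, with success 68% or 58%. One-sided error at 23% is 2.1% or 1.0%, so both stay below 2.5%. These figures assume independent binomial responses and exactly 56 analysed subjects.

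Separately, subjects whose responses may have helped choose the RP2D count in the test at that dose. The bias, if any, is upward. Its size cannot be derived from the documents, and the pooled subjects are at most 6/56 = 10.7% of the analysis. The protocol text has no prespecified estimate free of it. The documents do not support saying that the pooled result is materially inflated or that the pooled analysis is invalid. The analysis set for the pooled subjects needs only a clarifying sentence.

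**What to change.** 1. In Section 9.2.1.2 and the synopsis, state that the rule is a two-sided 95% Clopper-Pearson lower limit above 23% at the actual analysed N. Label 21/56 an illustration, and give the minimum counts: 19 at N = 50–53 and 20 at N = 54–56.
2. Keep the pooled analysis as the decision analysis. Prespecify the Phase 2-only ORR with its exact CI (at least 19 of 50 clears 23%) as a sensitivity analysis, reported beside any superiority statement.
3. Add one sentence to Sections 9.1.2 and 9.4.3 that pooled Phase 1b subjects are analysed in the FAS for this purpose.

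The cost is wording in the protocol and SAP and one extra table, with no extra subjects. The downside is that the two results will sometimes disagree: about 14.5% of trials at a true ORR of 38% even with no selection, largely because Phase 2 alone has the smaller N. The report should say so, so that a disagreement is not read as proof of bias.

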In addition, clinically important or persistent toxicities not included in the above criteria may be considered a DLT following review by the Sponsor and study Investigators. All DLTs should represent a clinically significant shift from baseline. These will be evaluated according to National Cancer Institute (NCI) CTCAE v5.0.

To fully characterize the safety of repotrectinib in combination with trametinib, subjects who are discontinued from treatment before completing the DLT evaluation period (28 days, Cycle 1) due to disease progression or other event unrelated to study drugs, or who did not adequately complete the PK evaluations within Cycle 1, may be replaced.

Determination of MTD

The MTD is defined as the highest dose level of repotrectinib given in combination with trametinib observed to cause a DLT in fewer than 33% of the treated subjects in the first treatment cycle (i.e., 28 days, Cycle 1).

Recommended Phase 2 Dose (RP2D) Definition

The RP2D is the dose chosen for further study in Phase 2 based on the Phase 1b results. RP2D dose selection will be based on the entirety of the safety, efficacy, and clinical pharmacology data using an integrated quantitative approach. The RP2D may be the MTD unless one or more of the following suggest an alternate dose below the MTD would be preferable:

- clinically significant anti-tumor effect (complete response [CR], partial response [PR], or prolonged stable disease [SD]) occurs below the MTD, in which case a clinically active dose level may be selected as the RP2D;
- the MTD is not achieved, in which case the highest dose level administered may become the RP2D; or
- toxicities observed beyond the DLT evaluation period (Cycle 1) require selecting the RP2D below the MTD level.

Once the MTD of repotrectinib in combination with trametinib has been determined, the RP2D will be determined at or below the MTD.

Phase 2 Study Design:

Once the MTD/RP2D of repotrectinib in combination with trametinib has been determined, approximately 50 subjects will be enrolled into the Phase 2 expansion portion. The Phase 2 portion is designed to explore the anti-tumor efficacy and safety of repotrectinib in combination with trametinib for the treatment of patients with locally advanced or metastatic non-small cell lung cancer (NSCLC)

harboring a *KRAS*^{G12D} mutation.

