KRAS mutations occur in 20–40% of lung adenocarcinomas, with the most frequent mutations occurring in codons 12 and 13, and the most common subtypes including *G12C*, *G12V*, and *G12D* ([Cox 2014](#); [Ricciuti 2016](#)). The presence of *KRAS* mutations is prognostic of poor survival for patients with NSCLC when compared to the absence of *KRAS*, independent of therapy ([NCCN 2020](#)). *KRAS* mutations are also predictive of lack of therapeutic efficacy with epidermal growth factor receptor (EGFR) tyrosine kinase inhibitors (TKIs).

Although there are clinically-approved inhibitors of several MAPK pathway proteins (e.g., inhibitors of MEK, BRAF and EGFR) for a subset of NSCLC patients, to date there have been no approved targeted therapies for treatment of *KRAS*-mutant NSCLC ([NCCN 2020](#)).

Recently, development of selective allosteric KRAS^{G12C} inhibitors such as AMG510 and MRTX849 have demonstrated encouraging clinical activity in patients with *KRAS*^{G12C}-mutant NSCLC, with overall response rates (ORRs) as high as 54% (N = 13) observed with AMG510 ([Amgen 2019](#); [Canon 2019](#); [Hallin 2019](#)). However, *KRAS*^{G12C} mutations are only present in a small subset of NSCLC patients (approximately 13% of lung adenocarcinoma harbor *KRAS*^{G12C} mutations) and KRAS^{G12C} inhibitors rely on the mutant cysteine for binding and therefore do not affect the wild-type KRAS protein or other KRAS subtypes. In addition, resistance to direct targeting of KRAS can occur and may be due to genetic alterations in downstream pathways, thus combination therapies are likely needed to provide greater benefit than direct targeting of KRAS alone ([Burns 2020](#)).

Taken together, there is an urgent, unmet medical need for development of novel targeted therapeutics and novel therapeutic strategies for the treatment of patients with locally advanced or metastatic *KRAS*-mutant NSCLC.

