Section 4.1, Inclusion Criteria #14	
 Subject must have a documented KRAS^{G12D} mutation as determined by a qPCR or NGS test performed in a CLIA laboratory or equivalently accredited diagnostic laboratory. 	
 Subject must have a documented KRAS^{G12D} mutation as determined by a qPCR or NGS test performed in a CLIA laboratory or equivalently accredited diagnostic laboratory. 
Local tissue-based or liquid biopsy diagnostic testing will be permitted.
	
Synopsis, Exclusion Criteria #10	10. History of extensive, disseminated, bilateral, or presence of CTCAE any grade interstitial fibrosis or interstitial lung disease including a history of pneumonitis, hypersensitivity pneumonitis, interstitial pneumonia, interstitial lung disease, obliterative bronchiolitis, and pulmonary fibrosis.	10. Currently have or had a history of ILD, radiation pneumonitis that required steroid treatment, or drug-related pneumonitis	Clarified exclusionary criteria for subjects who have or had a history of ILD.
Section 4.2, Subject Exclusion Criteria #10			
Synopsis, Criteria for Evaluation	Secondary Endpoints for Phase 1: 
 ORR assessed by BICR and Investigator using RECIST v1.1 Phase 2 Primary Endpoint: 
 ORR assessed by BICR per RECIST v1.1. Phase 2 Secondary Endpoints: 
 ORR by Investigator DOR, TTR, and CBR by BICR and Investigator. 	Secondary Endpoints for Phase 1: 
 ORR assessed by the Investigator using RECIST v1.1 Phase 2 Primary Endpoint: 
 ORR assessed by Investigator per RECIST v1.1. Phase 2 Secondary Endpoints: 
 DOR, TTR, and CBR by the Investigator Intracranial objective response rate (IC-ORR) assessed according to modified RECIST v1.1 in 	Since the study is a signal finding study, radiographic disease assessment by PI per RECIST v1.1 is sufficient to assess efficacy signal. BICR assessments will still be performed and may be analyzed.
Section 9.3, Study Endpoints			

Protocol Section	Original Text with Deletions	Revised Text	Justification																

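### Phase 2 has no comparator, so an exact lower limit above 23% cannot support the planned conclusion that the combination is superior to approved second-line chemotherapy

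*Combined protocol and SAP*

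**What the plan says.** Section 9.2.1.2, repeated under Sample Size Determinations in the synopsis, sets the criterion for a positive Phase 2 result. The illustration is 21 responders among 56 subjects (50 from Phase 2 plus up to 6 pooled from Phase 1b), with the condition "where the lower limit of the 95% CI is > 23" per cent. If it is met, "repotrectinib in combination with trametinib will be considered superior than the currently approved chemotherapy in the second-line setting for NSCLC"; the sentence then limits itself to this expansion cohort. The comparison includes docetaxel plus ramucirumab, "which has demonstrated a best ORR of 23% (95% CI: 20 – 26) in the second-line setting".

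Other sections describe a different kind of study. Section 3.1 calls it open-label. Section 5.1 allocates every subject to the combination. Section 3.3 says that the Phase 2 "portion is designed to explore the anti-tumor efficacy and safety of repotrectinib in combination with trametinib". Section 9.4.3.1 reports ORR with a two-sided 95% Clopper-Pearson interval and specifies no comparative test. Section 1.2.2 says that the presence of KRAS "mutations is prognostic of poor survival for patients with NSCLC".

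**The concern.** Superiority is a comparative claim, and this trial generates data on one treatment only. Under the stated rule, any difference between this cohort and the external patients is read as drug effect. The cohort is selected for KRAS G12D. The pooled Phase 1b subjects may have had up to three prior regimens (Section 4.1). Response is read by the investigator and must be confirmed. The reference is described only as a second-line figure. The plan does not say how its patients compare on these points, and it describes no matching or adjustment.

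The sentence is also the only place where the plan says what a positive final Phase 2 result would mean. If it stands, a single-arm estimate could be reported as a pre-specified finding of superiority over approved therapy. A secondary point is that the reference interval of 20 to 26% is printed but enters no calculation.

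**Working it through.** **Inputs.** N = 56, the example of 21 responders, the 23% cut-off and the reference interval of 20 to 26% come from Section 9.2.1.2. The interval method comes from Sections 9.2.1.2 and 9.4.3.1. The 38% target comes from Section 9.5.

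**1. The plan's own figure.** The Clopper-Pearson limits for x of n are the 2.5% quantile of Beta(x, n − x + 1) and the 97.5% quantile of Beta(x + 1, n − x). For 21/56 = 37.5% they are 24.9% and 51.5% (unrounded 51.45%). This reproduces the printed 38% (25 to 51), so the arithmetic is right.

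**2. Smallest result that meets the rule.** For 19/56 the lower limit is 21.8%, which fails. For 20/56 the interval is 23.4% to 49.6%, which passes. The limit criterion is therefore met at 20 responders, one fewer than the illustration, and both counts are carried below.

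**3. Chance of declaring superiority.** With X ~ Binomial(56, p), the upper tails are:

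| True ORR of the combination | P(X ≥ 20) | P(X ≥ 21) |
|---|---|---|
| 20% (lower reference limit) | 0.5% | 0.2% |
| 23% (reference estimate) | 2.1% | 1.0% |
| 26% (upper reference limit) | 6.9% | 3.9% |
| 38% (target) | 68% | 58% |

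The first three rows are errors if the reference rate for these patients equals the true ORR shown. These are fixed-sample figures. If the 15 interim subjects are counted within the 56 and the futility stop is applied, the 23% entries become 2.08% (from 2.14%) and 1.01% (from 1.03%).

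**4. Averaging over the reference's sampling error.** The half-width of 3 points gives a standard error of 3 / 1.96 = 1.53 points. Averaging the tail over p ~ Normal(23%, 1.53%) gives 2.5% for at least 20 responders and 1.3% for at least 21.

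**5. A two-sample check.** The documents do not give the size of the external sample. The printed interval implies about 0.23 × 0.77 × (1.96 / 0.03)² ≈ 756 patients, and a range of 600 to 850 was tried. Against 23% in a sample of that size:
- 21/56 differs by 14.5 points (Wald 95% interval about 1.4 to 27.6; Fisher p about 0.02).
- 20/56 differs by 12.7 points (about −0.3 to 25.7; Fisher p 0.035 to 0.049).

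This covers sampling error only. Nothing in steps 1 to 5 measures case-mix difference, and the documents hold no data from which it could be measured.

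**The case against.** The strongest reply is that comparing a single-arm Phase 2 with a historical rate is ordinary practice. The sentence sits in a sample-size section and confines itself to this cohort, the analysis section contains no superiority test, and Section 9.4.1 lets the SAP supersede. The plan also chose what it calls the best ORR as its reference. Much of this stands: 23% is a usable reference, and the limit rule is a reasonable screen. It does not rescue the verb. Confining the claim to the cohort still leaves a comparison with a treatment that the cohort did not receive, and nothing in the documents withdraws the sentence.

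Three stronger readings are tempting and are not supported.

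- A reader might infer that the printed reference interval overturns the example, because 24.9% lies between 20% and 26%. It does not. The rule's error averaged over that interval is about 2.5%, and 21/56 still differs nominally from an external sample of the implied size.
- A reader might infer that case mix flatters the drug. The documents give no basis for that direction. The one prognostic statement, in Section 1.2.2, concerns poor survival. If it carried over to response, which that section does not say, the relevant reference would be below 23% and the rule conservative.
- A reader might set the superiority wording against the signal-finding description in Appendix 2. That phrase appears only among the justifications in the change log. The point does not need it, because Section 3.3 already describes Phase 2 as exploratory.

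**Conclusion.** The point holds as a fault in the conclusion that the plan draws, not in its interval or its cut-off. A lower limit above 23% shows that the ORR in this cohort exceeds a reference value. It does not establish superiority over approved chemotherapy, whatever the responder count.

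Treating 23% as a constant is a secondary matter. Across the printed reference range the rule's error runs from 0.5% to 6.9% for at least 20 responders, or 0.2% to 3.9% for at least 21. Averaged over the reference's sampling error it stays at about 2.5% or 1.3%. These figures assume N = 56, independent binomial responses and a normal sampling distribution for the reference. The size and direction of any case-mix bias cannot be determined from the documents. Trial conduct is unaffected.

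**What to change.** In Section 9.2.1.2 and in the synopsis, replace the superiority statement with wording such as: *the lower limit excludes the reference ORR of 23%, and the combination will be considered to warrant further evaluation*. Keep 23% as the reference rate. Beside it, report the rule's error at 20%, 23% and 26% for the responder count that the sponsor intends as the criterion.

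This is a text change in two places plus a short table. It needs no extra subjects or procedures and leaves the rule's power unchanged. The downside is a more modest stated conclusion from a positive result.
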